Fixed versus conventional removable Twinblock for overjet reduction in children – A randomised clinical trial to investigate the burden of care

Signatures

The undersigned confirm that the following protocol has been agreed and approved by the Sponsor and that the Chief Investigator agrees to conduct the trial in compliance with this approved protocol and will adhere to the principles of GCP, the Sponsor SOPs, and any other applicable regulatory requirements as may be amended from time to time.

Wir Um

[name] Chief Investigator

Signature

09-02-2021 Date

[name] Principal Investigator

6.2

the [name]

Signature

09-02-2021 Date

[name] Individual Responsible for Statistical Review

Signature

15-01-2021 Date

LIST OF ABBREVIATIONS (including Trial abbreviations)

GCP	Good Clinical Practice
TMF	Trial Master File
SOP	Standard Operating Procedure
CRF	Case Report Form
ТСТИ	Tayside Clinical Trials Unit
GDC	General Dental Council
PI	Principal Investigator
CI	Chief Investigator
AE	Adverse Event
SAE	Serious Adverse Event
AR	Adverse Reaction
UAR	Unexpected Adverse Reaction
SUSAR	Suspected Unexpected Serious Adverse Reaction
CNORIS	Clinical Negligence and Other Risks Scheme
NRES	National Research Ethics Service
REC	Research Ethics Committee
QC	Quality Control
GP	General Practitioner (medical/dental)

SUMMARY

Trial Title	Fixed versus conventional removable Twinblock for overjet reduction in children – A randomised clinical trial to investigate the burden of care (FTB)				
Trial Design	Multicentre Randomised Clinical	Trial, two-arm parallel design			
Trial Population	Patients will be recruited from NHS primary care orthodontic practices and secondary care orthodontic units in Tayside and Grampian areas				
Sample Size	88				
Planned Trial Period	3.5 Years				
Clinical phase duration	3.5 Years				
Follow up phase duration	None				
Primary	Objectives Rate of overjet correction	Outcome Measures Overjet measurement in millimetres			
Secondary	 Objectives Skeletal change Dental change Soft tissue change Patient experience Cost effectiveness 	 Outcome Measures Lateral cephalometric analysis Tooth movement Facial volumetric analysis Experience questionnaire Number of visits/breakages 			
Inclusion Criteria	 Class II division 1 malocclusion No history of active orthodontic treatment Overjet >6mm (IOTN 4a/5a) Age 9-14 years Child & parent/carer who are able to assent and consent, respectively 				
Exclusion Criteria	 Overjet <6mm Mobile/loose deciduous teeth, Profound hypodontia affecting the incisor region (>1 missing tooth per quadrant) Subjects taking growth hormone or endocrine disorders Suspected or identifiable syndromes Subjects with cleft lip and palate Anterior open bite 				

1. INTRODUCTION

Prominent upper front teeth are associated with poor appearance of teeth, inadequate function and psychosocial problems along with an increased risk of trauma to teeth. Most patients with prominent upper front teeth do not like their facial appearance and this has been shown to be an important factor in evoking negative image and self-perception of one's body. It has been noted that the prevalence of bullying in children aged 11-12 years is 15% in the UK. More recently, the prevalence of bullying in children aged between 10 and 14 with malalignment of teeth has been shown to be 12.8% and was primarily noted to be in patients with prominent upper front teeth. Furthermore, teasing and bullving in relation to negative body image are the origin of most of the psychological problems that people are subjected to in later life. This tends to have impact on self-esteem and related quality of life. Children who receive brace treatment report improvements in quality of life and on completing treatment, they report an improved physical, psychological and social impact on their lifestyle. Prominent upper front teeth doubles the risk of trauma to the teeth and this has been calculated at a global level to 100-300 million traumatic injuries to teeth. Dental trauma is of considerable public health concern in the UK and research in Europe has shown the direct health care service costs for management of each traumatised permanent tooth are £240 and total costs (medicine and transport and loss of production) are £371

There are a variety of options for prominent upper front teeth in adolescents. The bite blocks (Twinblocks) invented by William Clark are a two-piece removable brace and these are frequently used in treatment. They work by harnessing the muscular forces to move the teeth and the jaws. Due to the growth potential in younger patients, response of the jaws to treatment can be greater and, in many cases, substantial prominence of upper front teeth can be fully corrected. Patients who wear the removable bite blocks on a full-time basis in the presence of active growth inevitably show an excellent treatment result, whilst those that fail to wear these, fail to produce any positive changes. The issue with compliance has been quantified by Parekh et al (2019) for the Twinblock appliance at mean daily wear of 12.38 hours or 51.6% of that recommended. The solution to the problem of compliance is to develop a fixed bite block appliance that is effective. The compliance, comfort and speed of treatment with fixed bite block brace treatment remains to be tested.

Hence in this clinical trial, we propose to compare the effects of the fixed and removable bite blocks (Twinblocks) in correcting upper prominent front teeth in 120 growing individuals aged between 09 to 14 years old. The speed of correction, changes to the teeth, jaws and face, cost effectiveness and psychosocial aspects of treatment will be studied amongst participants from Tayside and Grampians regions within Orthodontic specialist practices and Hospital services.

2. BACKGROUND AND RATIONALE

Class II division 1 malocclusion is characterised by a combination of skeletal, dental and softtissue factors. The most frequent permutation involves an increased overjet and retrognathic mandible combined with a degree of maxillary incisor proclination modulated by the soft tissues.

Class II division 1 malocclusion is associated with aesthetic, functional and psychosocial problems along with an increased risk of dental trauma. Most patients with a substantial overjet do not like their facial appearance and some have difficulty in biting certain types of food. As with Class III malocclusions and other dentofacial disproportions, Class II malocclusion has been shown to be an important factor in negative body image and negative self-concept. It has been noted that the prevalence of bullying in children aged 11-12 years is 15% in the UK (Boulton and Underwood, 1992). Boys are known to suffer direct bullying such as physical and verbal abuse, whilst girls endure indirect bullying such as malicious gossip and rumours (Baldry and Farrington, 1999). More recently, the prevalence of bullying in adolescents aged between 10 and 14 with a malocclusion has been shown to be 12.8% and was primarily noted to be in patients with Class II division 1 malocclusion. Moreover, adolescents who are bullied due to a malocclusion report a negative impact on both their self-esteem and oral-health-related quality of life (OHRQoL; Seehra *et al.*, 2011a). Furthermore, teasing and bullying in relation to negative body image are the origin of most of the psychological problems that people are subjected to in later life. The financial costs of the adverse effects of mental illness on people's quality of life

are estimated at £41.8 billion per annum, with 10% of children in the UK having a diagnosable mental health condition (National mental health development unit – factfile 3).

On the positive side, adolescents who receive orthodontic treatment report improvements in most OHQoL domains when assessed using the Child Perception Questionnaire 11- to 14-year olds and on completing orthodontic treatment, adolescents report an improved physical, psychological and social impact on their lifestyle relating to their occlusion (Bernabé *et al.,* 2008). An increased overjet doubles the risk of dental trauma and large overjets treble the risk of a traumatic dental injury. This has been calculated at a global level to 100-300 million traumatic dental injuries (Petti S 2015). Dental trauma is of considerable public health concern in the UK and research in Europe has shown the direct health care service costs for management of each traumatised permanent tooth are £240 and total costs (medicine and transport and loss of production) are £371.

There are a variety of options for managing a Class II malocclusion. These are classified as comprehensive, camouflage, compromise and monitoring/observation. Comprehensive treatment is offered to patients with a severe skeletal Class 2 relationship where a combination of orthodontic treatment and orthognathic surgery are used to produce a Class I occlusion on a Class I skeletal base relationship at the end of treatment. Where the skeletal relationship is less severe, premolar extractions and fixed appliances can camouflage the skeletal pattern and for patients who only want upper arch alignment, compromise treatment using an upper fixed appliance can deliver this on either an extraction or non-extraction basis with any residual overjet being left untreated. This option is the least stable whilst comprehensive treatment is more stable by virtue of correcting the relationships between the skeletal, dental and soft-tissue aetiological factors. Monitoring/observation is an appropriate strategy where there are no patient concerns, no desire for treatment or where the medical/dental health and/or treatment logistics preclude participation in treatment.

Functional appliances are frequently used for the treatment of Class II division 1 malocclusion by harnessing the muscular forces to move the teeth and the jaws. The American Dental Association describes them as "loose, usually removable intra-oral devices which alter the muscle forces against the teeth and craniofacial skeleton. These are dynamic appliances, which depend on altered neuromuscular action to effect bony growth and occlusal development. They are usually used in mixed dentition to treat pediatric malocclusions" (Glossary of American Dental Association, 1992). As such, functional appliances (and other growth modification techniques) straddle the comprehensive and camouflage categories. Due to the growth potential in younger patients, the skeletal response to treatment can be greater than with adolescent patients. In many cases with a substantial overjet (i.e. Index of Orthodontic Treatment Need categories 4 and 5), a Class I skeletal relationship can be produced at the end of treatment, particularly where a retrusive mandible is a key presenting feature. In adolescent patients the skeletal response is reduced with most of the occlusal change resulting from dentoalveolar compensation. Although the age at treatment has not been shown to influence the amount of skeletal change delivered by functional appliances in a single randomised controlled trial (O'Brien et al, 2009), a favourable vector and magnitude of growth underpins cases that are successful with orthodontic growth modification (Tulloch et al, 2004) and it is logical to harness this where possible.

Research has so far failed to identify the precise effects of functional appliances although the evidence points to additional skeletal growth being delivered for growing patients with Class II malocclusions. In randomised controlled trials, this has been quantified at 1-2mm (Keeling et al, 1998; O'Brien et al, 2003 a,b; Kinzinger & Diedrich, 2005; Cozza et al, 2006; Thiruvenkatachari et al, 2013). Furthermore, the enigma of the effects of functional appliances where some cases demonstrate dramatic skeletal changes whilst other cases show only a modest skeletal improvement is thought by the clinical community to result from the paradigm of compliance in addition to the positive contribution from active growth. Thus patients who wear removable functional appliances on a full-time basis in the presence of active growth inevitably show an excellent treatment result, whilst those that fail to wear removable functional appliances also fail to produce any positive dentoskeletal changes.

The Clark Twinblock is one of several functional appliances that have been invented by orthodontists for the treatment of Class II malocclusion. It was developed by William Clark in the 1980's as a two-piece functional appliance and is easier to wear than other single piece functional appliances. It is therefore now the most commonly used functional appliance in the UK for several reasons:

- relatively well tolerated by the patient
- robust and easy to repair
- compensatory expansion is easy using a midline screw
- suitable for mixed or permanent dentition treatment

A national UK survey in 2000 discovered that the following design principles are popular:

- Upper appliance: Adams' cribs for the upper first premolars and the upper first permanent molars, midline screw, blocks with optional labial bow.
- Lower appliance: Adams' cribs on lower first premolars and lower first molars, incisor capping and blocks.
- The division between upper and lower blocks at a steep angle of 70 degrees to the occlusal plane and should be mesial to the lower first molars, permitting removal of the lower molar crib and grinding of the upper block if accelerated eruption of these teeth is required.

However, like all removable functional appliances, compliance with the removable Twinblock appliance can be problematic. The issue with compliance has been quantified by Parekh et al (2019) for the Twinblock appliance at mean daily wear of 12.38 hours or 51.6% of that recommended. Furthermore, age is also a factor in compliance with O'Brien et al. (2003c) finding older patients had unusually high failure rates (34%) compared to younger patients (O'Brien et al. 2003a) at 19%. The solution to the problem of compliance is to use a fixed functional appliance. The oldest known fixed functional appliance is the Herbst appliance which was first described at the start of the 20th century and re-introduced by Hans Pancherz more recently. It is comprised of two maxillary and mandibular sections – either cast or banded. However, problems include breakages, regular re-cementing of the appliance, and patient acceptance. The most recent version of the Herbst appliance was used in the UK MRC-funded multicentre RCT (O'Brien et al. 2003c) comparing the removable Twinblock appliance with the Herbst. The rate of failure during the functional phase was surprisingly high in the Twinblock group at 34%, and much lower in the Herbst group at 13%.

Combining the extensive research literature on the Herbst appliance with clinical experience produces the following summary:

- The Herbst appliance reduces almost all overjets in 6 months which compares to an average of nine months with the removable Twinblock appliance
- Patients find the Herbst appliance not excessively intrusive after the first week like the removable Twinblock appliance
- There is an inconveniently high rate of decementation, mechanical failure and lower incisor proclination with the Herbst appliance
- A functional appliance that can be rapidly and reliably added to a conventional fixed appliance will probably prove very popular.

The Bass Dynamax appliance has been proposed as an alternative and an improvement to the Herbst appliance. It is a two-part appliance, with the interlock lingual to the occlusal surfaces of the teeth. The lower half can be fixed or removable and this design has some of the attributes of other appliances. Whilst it has potential advantages including theoretical incremental advancement resulting in greater co-operation and potentially greater contribution of mandibular growth than dentoalveolar effects, it remains un-resolved whether the Bass Dynamax is more efficient than other functional appliances as a substantial UK RCT involving this appliance and a Twinblock appliances has been abandoned due to excessive breakages of the Dynamax (Thiruvenkatachari et al.2010). This appliance is therefore not used widely.

The fixed design of the Twinblock appliance has three significant advantages when compared to a Herbst and Dynamax appliances:

• The appliance is significantly cheaper as no complex components are required for construction whilst the clinician involvement in treatment is no more complicated when compared to other removable functional appliances

- The appliance is located on the occlusal plane and not in the buccal sulcus, which assists robustness and patient comfort
- Because the two halves of the appliance are not permanently linked together, the problems of leverage on the fixation points does not arise.

However, the simplicity and versatility of the fixed Twinblock appliance in relation to accelerating functional appliance treatment times remains to be tested. Initial data from a scoping study (REC 17/ES/0126) shows significant difference in overjet reduction at 3 months treatment duration with the fixed Twinblock. The patient experience with the Fixed Twinblock did not report any negative experience in relation to soreness from the appliance. Free text comments from patients were positive for the use of the fixed appliance.

2.1 RATIONALE FOR TRIAL

The fixed design of the Twinblock appliance offers an opportunity to reduce treatment time using a simple and versatile device which is fixed, reducing the problems with compliance. Outcomes of this trial are clinically relevant with major dental health and financial benefits for the Scottish population and globally. This patient centred innovative research trial could potentially maximise correction of the malocclusion during growth and negate the challenges of dental trauma and malocclusion associated psychosocial problems in adolescents. The available evidence is presently limited and further high quality, well-designed clinical trials assessing the relative merits of both clinician and patient centred outcomes are needed (Pacha M M 2015). We are presently reviewing the literature further on effects of removable and fixed appliances on overjet correction and conducting a large network meta-analysis on the topic (Overjet correction in preadolescent and adolescent age groups: fixed versus removable appliances. PROSPERO 2018 CRD42018112703).

The aim of our trial is to investigate the speed of correction of the overjet (upper front teeth prominence) as well as the patient's perception of treatment and the associated changes, and experience with the fixed and removable Twinblock appliances.

3. TRIAL OBJECTIVES AND OUTCOMES

3.1 OBJECTIVES

3.1.1 Primary Objective

 Does the fixed Twinblock appliance accelerate overjet reduction for a Class II division 1 malocclusion in comparison to the conventional removable Clark Twinblock appliance?

3.1.2 Secondary Objectives

- 2. Does the fixed Twinblock appliance produce more skeletal than dentoalveolar contribution for a Class II division 1 malocclusion in comparison to the conventional removable Clark Twinblock appliance?
- 3. Does the fixed Twinblock appliance produce more facial volume increase in comparison to the conventional removable Clark Twinblock appliance?
- 4. Are patient's treatment experience better with the fixed Twinblock appliance as compared to the removable Twinblock appliance.
- 5. Is the fixed Twinblock appliance more cost effective and safer for correcting increased overjets as compared to the removable Twinblock appliances.

3.2 OUTCOMES

3.2.1 Primary Outcomes

1. Rate of overjet correction by comparing change in millimetre/month from clinical measurements with fixed and removable Twinblock appliances.

3.2.2 Secondary Outcomes

- 2. Relative skeletal, facial and dentoalveolar contributions to overjet correction by comparing lateral cephalogram changes via cephalometric analyses (Mills 1982), and facial volumetric changes (Camison et al 2018) and tooth movements by superimposing 3D scans, respectively, at the end of orthodontic treatment.
- 3. Patients' perception and experience with the fixed and removable Twinblock appliance will be assessed using the three questionnaires approach (Pre-Treatment questionnaire, Orthodontic Experience Questionnaire and Post-Treatment questionnaire (Al-Naseri et al 2017)
- 4. Cost-effectiveness of overjet reduction with fixed and removable Twinblock by comparing direct costs of treatment i.e., number of visits for Twinblock phase of treatment and number of breakages/loss with the fixed and removable Twinblock appliances.
- 5. Potential adverse effects of the fixed Twinblock and removable Clark Twinblock appliance.

Table 1: Primary Objectives and Outcome Measures

Primary Objective:	Outcome Measure:	Timepoint of outcome measured
Rate of Overjet correction	change in millimetre/month from clinical measurements	T0, T1, T2, T3, T4, T5

Table 2: Secondary Objectives and Outcome Measures

Secondary Objective:	Outcome Measure:	Timepoint of outcome measured
Skeletal, facial and dentoalveolar contributions to overjet correction	Lateral cephalometric analyses, Facial volumetric changes, and tooth movements by superimposing 3D scans	T0, T4, T5
Patients' perception and experience	Pre-Treatment questionnaire, Orthodontic Experience Questionnaire and Post- Treatment questionnaire	T0, T1, T4
Cost-effectiveness of treatment	Number of visits for Twinblock phase of treatment and number of breakages/loss	Τ4

4 TRIAL DESIGN

4.1 INTERVENTION

Participants will be treated either the fixed or removable Twinblock appliances. Following completion of the Twinblock treatment, all participants will continue treatment with fixed orthodontic appliance (train-track braces), which isstandard treatment protocol following completion of twinblock treatment.

[figure not shown]
4.2TRIAL DESCRIPTION

We plan to undertake a multicentre randomised clinical trial in Tayside and Grampian regions as a two-arm parallel design to detect a difference between the fixed and removable Twinblock appliance for overjet reduction.

			Time p	points		
Data collection	T0 Start	T1 3 months	T2 6 months	T3 9 months	T4 End of Twinblock treatment	T5 End of treatment
Clinical Orthodontic assessment	~				✓	~
Overjet measurement	~	~	\checkmark	~	✓	~
Lateral cephalogram	~				✓	✓ (near end)
Impressions / intraoral scan	~				✓	~
3D Facial Stereo – photogrammetry Image	~				✓	~
Patient Experience Questionnaire	\checkmark	~			~	

4.3 TRIAL MATRIX

4.4 TRIAL FLOWCHART

4.5 TRIAL ASSESSMENTS

Trial assessments will be as described in the trial matrix at 4.3 at all the recruiting sites (primary and secondary care sites). Standard NHS clinical treatment protocol with Twinblock appliance includes a phase of further fixed orthodontic treatment (train track braces) and will be part of the treatment for all participants in this trial. Whilst the primary objective of the trial is to compare the fixed and removable Twinblocks, it is appreciated that skeletal, dental and soft tissue effects could change by the end of fixed orthodontic treatment (T5). Therefore, all data (excluding patient experience questionnaire) will be collected up until T5. To collect experience of participants with Twinblock phase of treatment alone, the patient experience questionnaires will be collected up until T4.

4.6 TRIAL SAFETY ASSESSMENTS

This is a low risk trial, and no serious adverse events are anticipated. However, it is possible that there may be allergic reactions to the Twinblocks and this will be recorded as an expected adverse event in the CRF. The Twinblock appliance treatment will be discontinued in case of allergic reaction and discontinued from the trial and other options for management of the increased overjet will be provided. The site PI will report any SAE that is both related to the research procedures and is unexpected to the CI and the CI will send an NRES Safety Report to the appropriate REC within 15 days of becoming aware of the event. A copy of the Report will be sent in parallel to the Sponsor. An annual progress report will be submitted to the appropriate REC and a copy of the Report will be sent in parallel to the Sponsor.

Consideration and potential impact of the trial following the peak of the COVID-19 pandemic have been mitigated to ensure safety of participants and staff. The visits for treatment during the trial will be part of routine non aerosol generating dental care, with physical access to the dental hospital/orthodontic practice complying with Scottish government restrictions on social distancing. This information will be provided to participant and parent/carer prior to attendance and suitably prepared ahead of their appointment so that total contact time spent in the dental hospital/ orthodontic practice is reduced. Covid-19 screening will be undertaken ahead of the visit where possible and a high level of hand hygiene will be adopted with the provision of antiseptic hand gel on entrance and exit. To reduce contamination, minimised wait times in common areas will be adopted and safe entry/exit will be ensured with appropriate signage. Face coverings will be required to be worn where indicated by Scottish government guidance.

Radiographs are part of routine clinical investigations. Effective Dose per lateral cephalogram - 0.004mSv (from HPA-CRCE-012 'Frequency and Collective Dose for Medical and Dental X-Ray Examinations in the UK, 2008'). As the patients in this study are 9-14 years old, the risk is age corrected to 11% per Sv. The combined risk of cancer mortality from both exposures in this study is of the order of 1 in 1.1 million

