11.2 RECORDING AND REPORTING AES AND SAES

All AEs and SAEs will be recorded from the time a participant consents to join the trial until the last visit and will be assessed for severity by the CI or delegate. Participants with unresolved AEs at the last visit will be followed up until resolution or 30 days after last patient, last visit (LPLV), whichever is sooner. The CI or clinical trial investigator will ask about the occurrence of AEs and hospitalisations at every visit during the trial.

The Investigator will make a clinical judgment as to whether an AE is of sufficient severity to require the participant's removal from the study. A participant may also voluntarily withdraw from treatment due to what he or she perceives as an intolerable AE. If either of these occurs, the participant should, if required, be offered an end of trial assessment and be given appropriate care under medical supervision until symptoms cease, or the condition becomes stable. AEs/SAEs will be followed up until 30 days after participant's last visit.

The CI or delegate will ask about the occurrence of AEs/SAEs and hospitalisations at every visit during the study. SAEs which are both unexpected and related to study participation will be submitted on an HRA NCTIMP Safety Report form to the REC by the CI, within 15 days of becoming aware of the SAE, and copied to the Sponsor Research Governance Office.

Worsening of the condition under study will not be classed as an AE but will be defined as an outcome. Elective admissions and hospitalisations for treatment planned prior to randomisation, where appropriate, will not be considered as an AE. However, AEs/SAEs occurring during such hospitalisations will be recorded.

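### A child who stops the appliance for an allergic reaction or another adverse event can be taken out of outcome follow-up without having withdrawn consent

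*Protocol*

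**What the plan says.** **Stopping rules.** Section 4.6 (Trial Safety Assessments) states: "The Twinblock appliance treatment will be discontinued in case of allergic reaction and discontinued from the trial". The reaction is recorded in the CRF as an expected adverse event, and other ways of managing the overjet are then provided. Section 11.2 asks the investigator to judge whether an adverse event is of "sufficient severity to require the participant's removal from the study". Its next sentence covers a participant who chooses to withdraw from treatment. Both cases have the same consequence: "the participant should, if required, be offered an end of trial assessment", together with care until the symptoms end or the condition settles.

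**Adverse event recording.** Section 11.2: "All AEs and SAEs will be recorded from the time a participant consents to join the trial until the last visit". Unresolved events are "followed up until resolution or 30 days after last patient, last visit (LPLV), whichever is sooner". A later sentence in the same section gives a different end point: "AEs/SAEs will be followed up until 30 days after participant's last visit".

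**Outcome schedule.** Section 4.5: "all data (excluding patient experience questionnaire) will be collected up until T5". Table 1 in section 3.2.2 puts the primary outcome at "T0, T1, T2, T3, T4, T5". Section 6.1 has overjet measured with a ruler at every appointment.

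**Withdrawal and analysis.** Section 5.5.3 treats withdrawal and dropout as one category. Within 3 months no further records are taken; after 3 months an overjet measurement is attempted. It also requires that those who leave be described, with their reasons and how these relate to treatment and outcome. Sections 5.5.3 and 8.3 both promise an intention-to-treat analysis with imputation of incomplete data.

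**The concern.** Stopping an appliance and leaving a trial are different events. The first is a clinical decision. The second should normally need the family to withdraw consent, or contact to be lost. If an adverse event ends both together, outcome readings that could still have been sought are not taken, and the reason they are missing is linked to the device under study. Imputation then stands in for data that were obtainable, although an intention-to-treat analysis aims to follow every randomised child as allocated.

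This belongs in the protocol rather than in an analysis plan. An analysis plan can choose how to handle missing readings, but it cannot recover readings that were never taken.

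**Working it through.** **1. What 4.6 does.** The grammatical subject of the sentence is the appliance treatment, so the wording is loose. But the sentence first stops the treatment and then adds a second discontinuation, from the trial. Unless that addition takes the child out of the trial, it says nothing new.

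**2. What 11.2 does.** It has two terms, removal from the study and withdrawal from treatment. Both lead to the same step: one assessment, if required, plus clinical care. The terms are separate; the consequences are not.

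**3. Does another section restore follow-up?** Section 5.5.3 does not say whether it covers removal by the investigator. If it does, an exit within 3 months yields no further records and a later exit yields an attempted overjet reading. Section 6.1 implies a reading at the visit where the reaction is seen, because overjet is measured at all appointments. No section puts the child back on the remaining schedule.

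**4. Readings at stake per child.** Overjet time points after baseline: T1, T2, T3, T4, T5 = 5. Once the appliance has stopped, T4 as defined in 6.1 no longer applies, and T5 exists only if fixed appliance treatment follows. The recoverable readings are therefore those of T1–T3 still due, plus T5 in some children.

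| Exit | Scheduled readings ended (maximum) | Recoverable if the child attends |
|---|---|---|
| Before T1 | 5 | 3–4 |
| T1 to T2 | 4 | 2–3 |
| T2 to T3 | 3 | 1–2 |
| After T3, before T4 | 2 | 0–1 |

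These are maxima, because 6.1 lets time points be skipped once the overjet has reduced.

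**5. Number of children.** The protocol gives no allergy rate and no rate of exit for adverse events. At assumed rates of 1% and 2%: 88 × 0.01 = 0.88 and 88 × 0.02 = 1.76 children.

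**6. Scale against the sample size (section 8.1).**
- The plan's figures reproduce. For a difference of 81 days and an SD of 101 days, with alpha 0.05 (taken as two-sided) and 80% power, the t-test needs 25.4, so 26 per arm. Allowing for 40% loss, 26 / (1 − 0.40) = 43.3, so 44 per arm and 88 in total.
- The allowance is 88 − 52 = 36 children. The assumed exits are 0.88 / 36 = 2.4% to 1.76 / 36 = 4.9% of it.
- If 40% were lost in full, 88 × 0.60 = 52.8 children would remain (26.4 per arm, power 0.82). Losing two more on top leaves 50.8 (25.4 per arm, power 0.80). The allowance may already include such exits.

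The sample size is therefore not in question.

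**The case against.** The strongest reply is that this affects a handful of children at most and that the protocol already softens it. The trial is described as low risk and allergy as only possible. The triggering reaction is recorded, overjet is measured at all appointments, a reading is attempted after 3 months, withdrawals are described with their reasons, and 11.2 provides an end of trial assessment and adverse event follow-up. Removal under 11.2 is at the investigator's discretion, not automatic. Later readings would also reflect another treatment or none, while the primary outcome is the rate of correction with the two Twinblocks. Whether to collect them is partly a choice about the question being asked.

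Most of this stands, and it keeps the point minor. It does not remove it: the safeguards give at most isolated readings, and none keeps the child on the schedule.

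A reader might infer four stronger things that the protocol does not support.

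- *The comparison between arms is biased.* Allocation is known to the site, so a removal decision could be influenced by arm, but nothing shows that exits will be frequent or will differ by arm.
- *Safety information on the device is lost.* The triggering event is kept and unresolved events are followed. At most, events first appearing after the exit go unrecorded, and even that assumes the exit counts as the last visit, which 11.2 does not say.
- *Section 4.5 is flatly contradicted.* Its statement about T5 explains why collection runs beyond the Twinblock phase; it makes no explicit promise about children who stop early.
- *All five readings are lost.* That is the ceiling for a child who leaves before T1.

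**Conclusion.** The point holds as a minor one. Sections 4.6 and 11.2 allow outcome collection to end for a treatment-related reason while consent still stands, and nothing elsewhere keeps the child on the overjet schedule. This is a poor match for the stated intention-to-treat aim.

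The number affected is unknown and probably very small. The figure of one or two children rests on the assumed 1–2% exit rate, and the per-child counts are upper limits. The conclusion also rests on the natural reading of a loosely worded sentence in 4.6. The bias cannot be sized, because the protocol gives no exit rate and names no imputation method. No conclusion of the trial is shown to be at risk.

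**What to change.** Leave the clinical decision to stop the appliance as it is, and change three places.

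- **Section 4.6:** delete the second half of the clause, which takes the child out of the trial.
- **Section 11.2:** replace removal from the study with discontinuation of the allocated appliance. Then add: *Unless consent is withdrawn, overjet is measured at the stop visit and, where the child attends, at the remaining time points that still apply (T1–T3, and T5 if fixed appliance treatment follows). Recording of adverse events continues. The child is analysed in the allocated arm, and readings after a change of treatment are flagged.*
- **Section 5.5.3:** state that the 3-month no-records rule does not apply to these children.

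The cost is a few words and a ruler reading where the child attends. Attendance cannot be guaranteed, since 4.6 promises only that other management will be provided. The drawback is that overjet after the switch partly reflects the later treatment, so the flag is needed. How those readings enter the primary comparison should be set in the analysis plan.
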